13.1.5.1. Association of Biochemistry with Clinical Outcomes and Clinical Benefit

The association between biochemistry including ALP and bilirubin with clinical outcomes will be assessed and the clinical benefit of OCA using biochemistry as a surrogate endpoint will be evaluated. Detailed analysis will be described in the SAP.

Based on the association between biochemical changes and clinical outcomes described above, clinical benefit of OCA using biochemistry as a surrogate endpoint for key subpopulations of interest will be evaluated. This analysis will be further described in the SAP.

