Serum Chemistry	Albumin, blood urea nitrogen (BUN), creatinine, direct bilirubin, total bilirubin, aspartate aminotransferase [AST, SGOT], alanine aminotransferase [ALT, SGPT], ALP, GGT, electrolytes [calcium, chloride, potassium, sodium], glucose, total protein, and blood lipids (total cholesterol, LDL, HDL and very low density lipoprotein [VLDL] fractions and triglycerides [TG]), magnesium, phosphorus, bicarbonate, unconjugated (indirect) bilirubin, conjugated (direct) bilirubin, free fatty acids
Hematology	Hemoglobin, hematocrit, white blood count with differential, neutrophils, lymphocytes, monocytes, eosinophils, basophils, platelets, red blood cell count (including MCV, MCH, MCHC)
Coagulation	Prothrombin time (PT), partial thromboplastin time (PTT), international normalized ratio (INR)
Urinalysis	pH, specific gravity, total protein, glucose, ketones, bilirubin, blood, microscopic exam, urobilinogen, albumin, creatine, leucocytes, nitrates, albumin/creatinine ratio (if positive)
Biomarkers of Hepatic Fibrosis and/or Inflammation	IgM, C-reactive protein (CRP), TNF- α , FGF-19, CK-18, ELF, and others as determined during course of study
Genetics	DNA including single-nucleotide polymorphisms (SNPs) that may be involved in PBC; RNA
Blood Sample for Future Analysis	PBC autoantibodies and other cytokines and interleukins TBD
Other	OCA (parent and conjugates [glyco and tauro], OCA-glucuronide) and C4

The Investigator should manage subjects with clinically significant lipoprotein abnormalities using local standard of care procedures as appropriate after assessing the individual subject's total cardiovascular risk profile.

Urine-based β -hCG pregnancy tests will be performed in female subjects of childbearing potential per protocol specified visits. If a urine pregnancy test is positive, a serum pregnancy

test must be performed to confirm the result. If positive, the Sponsor must be notified and the subject will be followed, as outlined in [Section 12.1.11](#) through pregnancy outcome.

MELD scores, Child-Pugh score, and MRS will be calculated at screening, and at quarterly (MELD and Child-Pugh scores) or semi-annual (MRS) visits based on serum chemistry and coagulation.

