13.1.2. Determination of Sample Size

The target population is subjects who are at higher risk of liver-related clinical complications. Eligible subjects will have a diagnosis of PBC with bilirubin levels $>ULN$ and $\leq 5x ULN$ and/or $ALP > 3 \times ULN$. The following assumptions were used in sample size calculations:

- Exponential survival curves, placebo survival estimate of 0.6 at 8 years with a hazard ratio of 0.60, and total study duration of 10 years (from first subject enrolled), allowing for 4 years of subject accrual and 6 years of follow up.
- Subjects will be randomized in a 1:1 ratio to placebo or OCA.
- The 2 groups will be compared using a 2-sided log rank test at the 5% level of significance.
- Two interim analyses and one final analysis are planned. The first interim analysis will be performed when 50% of the target events are accrued and the second interim will be performed when 75% of the target events are accrued.
- A dropout rate of 10% is assumed

Based on the randomization ratio, significance level, and assumed hazard ratio, a total of 127 events (both groups combined) will provide 80% power to demonstrate a statistically significant difference between OCA and placebo on time to liver-related outcomes, including all-cause mortality.

In addition, based on the remaining assumptions stated above, it is estimated that approximately 428 subjects will be enrolled to attain 127 events.

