13.1.3. Primary Efficacy Analysis

The primary efficacy endpoint will be the time to first occurrence of one of the following post-randomization:

- Death (all-cause)
- Liver transplant
- MELD score ≥ 15
- Hospitalization (as defined by a stay of 24 hours or greater) for new onset or recurrence of:
 - Variceal bleed
 - Hepatic encephalopathy (as defined by a West Haven score of ≥ 2)
 - Spontaneous bacterial peritonitis (confirmed by diagnostic paracentesis)
- Uncontrolled ascites (diuretic resistant ascites requiring therapeutic paracentesis at a frequency of at least twice in a month).

The primary efficacy analysis will compare OCA to placebo with respect to the primary efficacy endpoint using the ITT population. Only adjudicated events will be included in analyses. The 2 treatment groups will be compared using the log rank test stratified by the randomization stratification factor. Kaplan-Meier (KM) estimates of the distribution of the time-to-event will be tabulated and graphed by treatment group. The tabulation will include the KM estimate of the medians and corresponding 95% confidence intervals (CIs), if the medians can be estimated. The number and percent of subjects censored and with events will be presented. The hazard ratio and 95% CI will be determined based on a Cox regression model stratified by randomization strata to estimate the magnitude of the effect. The same analyses for primary efficacy endpoints will be performed for PP population as a sensitivity analysis.

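### If clinical outcomes include MELD ≥15, as Sections 6.1 and 13.1.12 use the term, the bilirubin–outcome association in Section 13.1.5.1 is partly built in

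*Protocol*

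**What the plan says.** Section 13.1.5.1 of the protocol plans that "The association between biochemistry including ALP and bilirubin with clinical outcomes will be assessed". It then plans to evaluate the benefit of OCA with biochemistry as the surrogate, in the whole study and in key subpopulations. It does not itemise the outcomes, and it refers to the SAP twice for detail.

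Four other places bear on what the outcomes are and how they are used:

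- Section 6.1 states the primary objective as an effect on clinical outcomes, measured by a composite. Section 13.1.3 repeats the list, which includes "MELD score ≥ 15".
- Section 13.1.12 places the interim analyses at 50% (64) and 75% (96) of clinical outcome events.
- Section 12.2.7 says that "MELD scores, Child-Pugh score, and MRS will be calculated at screening, and at quarterly" or semi-annual visits from serum chemistry and coagulation results. Table 11 in that section lists total bilirubin under serum chemistry.
- Section 13.1.11 makes a strong correlation between biochemistry and clinical outcomes, in the total population, the condition for estimating the reduction in risk that goes with biochemical improvement in subpopulations.

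**The concern.** A surrogacy analysis asks whether movement in a marker predicts events that matter in their own right. If the marker is also an input to one of the events, some association must appear even when the marker predicts no death, transplant or decompensation. A rise in bilirubin pushes subjects over the MELD threshold by arithmetic, and a fall keeps them below it.

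What is at stake is the use made of the result. Built-in correlation makes the condition in Section 13.1.11 easier to meet. It also inflates the risk reduction then read across to subgroups, for which the trial has few events of its own. A fall in bilirubin may well reflect real improvement, but an analysis that counts MELD ≥15 cannot separate that from the arithmetic.

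**Working it through.** **1. The plan's own figures.** Inputs from Section 13.1.2: "The 2 groups will be compared using a 2-sided log rank test at the 5% level of significance"; "Exponential survival curves, placebo survival estimate of 0.6 at 8 years with a hazard ratio of 0.60"; "allowing for 4 years of subject accrual and 6 years of follow up"; 1:1 allocation; 10% dropout.

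- Events, fixed design: 4 × (1.960 + 0.842)² / (ln 0.60)² = 120.3, so 121.
- With Lan-DeMets O'Brien-Fleming looks at 64, 96 and 127 events, the requirement is 124.1. At 127 events power is 80.9%, against the statement that "a total of 127 events (both groups combined) will provide 80% power".
- Subjects: the event probability per arm is 1 − (e^(−6λ) − e^(−10λ))/(4λ), with placebo λ = −ln(0.6)/8 and OCA λ equal to 0.6 times that. The average is 0.3308. Then 127/0.3308 = 384, and 384/0.9 = 427, against 428 stated.

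These figures are sound and the point does not touch them.

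**2. What the term covers.** 0.50 × 127 = 63.5 and 0.75 × 127 = 95.25, which round up to the 64 and 96 in Section 13.1.12. Section 7.1 describes the 127 as adjudicated primary endpoint events. So the statistical section itself uses clinical outcome events for the composite that contains MELD ≥15, as Section 6.1 does.

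**3. The overlap (assumed formula).** The protocol gives no MELD formula. Assume the standard one with creatinine at 1: MELD = 3.78 ln(bilirubin) + 11.2 ln(INR) + 6.43, bilirubin in mg/dL. Appendix C gives a total bilirubin ULN of 1.2 mg/dL. Bilirubin alone brings MELD to 15 at:

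| INR | Bilirubin, mg/dL | Multiple of ULN |
|---|---|---|
| 1.0 | 9.7 | 8.0 |
| 1.2 | 5.6 | 4.7 |
| 1.3 | 4.4 | 3.7 |

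Section 8.3 excludes MELD above 12 at entry. From 12, the rise in bilirubin that alone reaches 15 is e^(3/3.78) = 2.2-fold.

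**4. Direction and possible size (illustration).** The documents do not give the share of first events that would be MELD ≥15, so 20% to 60% is assumed. In a simulation of 20,000 subjects over 8 years, about 30% had an event. Log-bilirubin followed a straight line with a subject-specific slope, a MELD event occurred when that line crossed the threshold, and all other events were independent of bilirubin. A Cox model gave these hazard ratios per SD of slope, adjusted for baseline:

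| Assumed MELD share | Composite with MELD | Without MELD |
|---|---|---|
| 0% | 0.99 | 0.99 |
| 20% | 1.47 | 1.01 |
| 40% | 2.36 | 1.02 |
| 60% | 4.33 | 1.01 |

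The true association is nil in every row. The slopes, INR values and shares are all assumed, and bilirubin is measured without error, which favours a strong artefact. Only the direction carries over to the trial.

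**The case against.** The strongest reply is that Section 13.1.5.1 never says MELD ≥15 is counted and leaves the detail to a SAP that is not at hand, which may already use a MELD-free outcome. The term is also not used uniformly. Section 11.1.2 applies it to individual components, transplant and death, and the reporting list in Section 12.1.6 names end-stage liver disease but no MELD threshold. The only text that tied this analysis to the primary composite by name is in the summary of changes; it is superseded and is not relied on here.

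Much of this stands. That MELD ≥15 is counted is an inference from Sections 6.1 and 13.1.12, not a statement in Section 13.1.5.1. The analysis is exploratory, since Section 13.1.10 treats everything outside the hierarchy as descriptive. The subgroup step is conditional and speaks of evaluating benefit, not of claiming it. MELD-free results are also planned elsewhere: transplant or death is a key secondary endpoint, and each component is analysed separately.

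Deferral does not answer the point in full. The protocol already states the outcome term, the marker and the use to be made of the association, and followed as written that combination is circular. The MELD-free endpoints are not named as the outcome for this analysis.

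A reader might also be tempted to turn a given fall in bilirubin into a percentage of outcomes removed, from the chance that one visit reads 15 or more. The documents do not support that. The endpoint is time to first adjudicated event over quarterly measurements for about 6 years or more, and neither the visit-to-visit variability nor the distribution of MELD is given.

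**Conclusion.** The concern holds in a limited form. On the natural reading of the protocol's own term, the bilirubin–outcome association in Section 13.1.5.1 is partly built in, and Section 13.1.11 depends on that association. This rests on two assumptions: that the term carries its meaning from Sections 6.1 and 13.1.12, and that total bilirubin enters MELD as in the standard formula.

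The size cannot be computed from the documents. The simulated hazard ratios of about 1.5 to 4.3 show what a purely arithmetic link could produce; they do not estimate what this trial will show.

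Two wider readings are not supported. The point does not show that bilirubin is a poor surrogate, only that this analysis could not tell. Nor does it reach ALP directly, or the randomised primary comparison, alpha, the 127 events or the 428 subjects at all.

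**What to change.** Add one sentence to Section 13.1.5.1 and cross-reference it in Section 13.1.11. It should state that the bilirubin association and surrogacy analysis uses the primary composite without MELD ≥15: death, liver transplant, hospitalisation for variceal bleed, hepatic encephalopathy or spontaneous bacterial peritonitis, and uncontrolled ascites. Show the MELD-inclusive version alongside, so that the difference between the two is visible. The SAP should carry the same definition.

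No new data are needed, because these events are already collected and adjudicated. The cost is one further model run and fewer events, hence wider intervals, in an exploratory analysis.

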13.1.6. Exploratory Efficacy Analyses

13.1.6.1. Responder Analyses

The percentage of subjects with a decrease in ALP of $\geq 15\%$ and $\geq 40\%$ from Baseline will be summarized by treatment group. In addition, the percentage of subjects with ALP \leq ULN will be summarized by treatment group.

The percentage of subjects that meet the criteria of a responder based on each of the definitions below will be summarized by treatment group. The response classification at baseline will also be included in the summary:

- ALP ≤ 3 x ULN and AST ≤ 2 x ULN and total bilirubin \leq ULN ([Corpechot 2008](#))

- ALP $\leq 1.5x$ ULN and AST $\leq 1.5x$ ULN and total bilirubin \leq ULN ([Corpechot 2011](#))
- ALP $\leq 1.67x$ ULN and total bilirubin \leq ULN ([Momah 2012](#))
- Normal bilirubin (values \leq ULN) and normal albumin (values \geq lower limit of normal) ([Kuiper 2009](#))
- ALP $\leq 1.76x$ ULN ([Kumagi 2010](#))

Responder analyses will compare treatment groups using a Cochran–Mantel–Haenszel test stratified by the randomization stratification factor. Missing values will be considered as a non-responder.

13.1.7. Pharmacoeconomic and Health Outcomes Endpoints

Sufficient data will be collected on resource utilization and quality of life to undertake cost-effectiveness analyses that are relevant to the major countries taking part in this study. Resource utilization data on hospitalizations, healthcare provider visits, and medications will be combined with appropriate national unit costs to calculate a cost per patient per year in the study.

Quality of life data from patient-reported outcomes measures will be combined with survival data to calculate quality adjusted time in the study per patient. Cost-effectiveness analyses will report the incremental cost per major clinical outcome averted, liver-related death averted, life-year gained and quality-adjusted life year gained, including OCA as part of usual care versus usual care without OCA. Analyses will be conducted within the study and using a lifetime perspective. A separate economic analysis plan will be prepared and reported separately from this protocol.

13.1.8. Supportive Analysis

Per the International Conference on Harmonisation (ICH) E10 guidance, “where no obvious single optimal external control exists, it may be advisable to study multiple external controls”. In order to address the risks associated with the inclusion of a long-term placebo arm, supportive analyses of the primary endpoint will compare clinical outcomes in the OCA treatment arm to historical controls, which serves as an external control for supportive analysis.

In an attempt to avoid the inherent biases with historical controls and to maintain the integrity of this comparison, one can invoke matching methods to optimize comparability and find a historical control that is “similar” to a participating subject. The historical database control should be as similar as possible to the study population and should have been exposed to a similar standard of care (see [Section 5.5.2.3](#)).

A propensity score can be used to reduce bias through matching, stratification, regression adjustment, or some combination. Propensity scores use information from a pool of patients who do not participate in the study (historical controls) to identify what would have happened to participating subjects in the absence of the treatment. By comparing how outcomes differ for treated subjects relative to historical controls, it is possible to estimate the effects of the treatment between the treated subjects and the matched natural history subjects.

A full range of covariates across which the treatment and historical controls might differ will be considered to mitigate potential bias. Although the results of using matching controls are conditional only on the observed covariates, if one has the ability to measure many of the

covariates that are believed to be related to the treatment assignment, then one can be fairly confident that approximately unbiased estimates for the treatment effect can be obtained. Both UK-PBC Group and the Global PBC Study Group formally collect numerous covariates that could be used for propensity score estimation including standard of care, eg, UDCA.

Historical controls will be chosen based on the same inclusion/exclusion criteria where possible. Propensity scores will be estimated using the available covariates that predict receiving the treatment. Only covariates and not outcome variables will be included in the propensity score estimation, to avoid biased results that are in favor of one treatment.

The covariates and factors collected in the historical databases will be specified in the SAP.

Propensity scores will be estimated first through a logistic regression model with treatment group as the dependent variable and the above covariates/factors as independent variables. Then the stratum boundaries are determined based on the propensity score values for both groups (OCA population and control [historical and randomized placebo]) combined or in the OCA population or historical control group alone. Based on recommendations in the literature, quintiles of the estimated propensity score from the combined group will be used to determine the stratum boundary cut-offs for the different strata.

The baseline characteristics between treated and natural history subjects in the matched dataset will be summarized and presented in a tabular format. Statistical methods such as Wilcoxon Rank-Sum test will be used to assess the balance for baseline covariates. The standardized difference and variance ratios for these covariates will also be calculated. In addition, box plots of propensity scores for treated and natural history subjects will be separately presented, to further assess the adequacy of matching.

A third-party statistician(s) will perform the propensity score modeling and matching. This third-party statistician(s) will be separate and independent from the statistician(s) who will assess the success of matching and perform efficacy analyses. Outcome events collected in the historical database are: death (liver-related and all-cause), liver transplant, HCC, and other. Other is defined as cirrhosis or decompensation such as ascites, variceal bleed, and encephalopathy.

The propensity score quintile will be then be used as the stratification factor in the stratified log rank test to compare randomized OCA-treated subjects in the ITT population and historical controls (Overall Historical Control Population: both the UK-PBC Group and Global PBC Study Group databases) on the following outcomes:

- Time to death (all-cause)
- Time to liver-related death
- Time to liver transplant
- Time to liver transplant or death (all-cause)
- Time to liver transplant or liver-related death

KM estimates of the distribution of the time-to-event will be tabulated and graphed by treatment group. The tabulation will include the KM estimate of the medians and corresponding 95% CIs if the medians can be estimated. The number and percent of subjects censored and with events

will be presented. The hazard ratio and 95% CI will be determined based on a Cox regression model stratified by randomization strata to estimate the magnitude of the effect.

Sensitivity analyses will be conducted limiting to the separate individual historical control databases, ie, UK-PBC Group and Global PBC Study Group. To evaluate the robustness of the propensity score estimations, additional algorithms and factors may be considered.

Although the study is designed as a placebo-controlled study, the DMC may recommend changes to study conduct based on the pre-specified interim analyses (see [Section 13.1.12](#)), including the potential use of a revised primary efficacy analysis. This analysis would compare all subjects in the OCA population, to all control subjects (randomized placebo and historical controls) on time to liver transplant or death (all-cause), using similar statistical methodology as specified above.

Notably, the planned primary analysis would not be revised without prior agreement with regulatory authorities.

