7. INVESTIGATIONAL PLAN

7.1. Overall Study Design

This is a Phase 4, double-blind, randomized, placebo-controlled, multicenter study. Eligible subjects will have a diagnosis of PBC with bilirubin levels of $>ULN$ and $\leq 5x ULN$ and/or ALP $>3x ULN$. Subjects enrolled will be at higher risk of liver-related clinical complications.

Approximately 428 subjects meeting all enrollment criteria will be recruited into the study over an approximate 4-year period, randomly allocated to treatment with either OCA or matching placebo in a 1:1 ratio (Figure 1). Subjects will be screened during a 1- to 8-week Screening period prior to entering the study to allow for the collection of repeat serum chemistry samples (at least 2 weeks apart) to confirm pretreatment ALP and total bilirubin values (refer to Section 9.7.6). Randomization will be stratified by UDCA treatment (yes/no) and baseline bilirubin categories ($>ULN/\leq ULN$). A minimum of 30% of subjects will have elevated bilirubin ($>ULN$) at Screening. In addition to the placebo control arm, multiple historical control groups (concurrent and retrospective) will be used.

Subjects will be dosed according to their cirrhosis status and Child-Pugh Score. Subjects who are noncirrhotic or classified as Child-Pugh A at Screening will initiate investigational product once daily with 5-mg OCA or matching placebo. Following 3 months of once daily treatment with investigational product, the dose should be titrated to a maximum 10 mg OCA or matching placebo once daily, based on tolerability and biochemical response (see Section 7.3).

[figure not shown]
Subjects with cirrhosis (see Section 9.7.3) and classified as Child-Pugh Class B or Child-Pugh Class C will follow a modified dosing regimen, and will initiate investigational product once weekly with the 5-mg OCA or matching placebo dose. In addition, these subjects will follow a modified titration plan, which is outlined in Appendix A.

It is anticipated that subjects will be followed for a minimum of approximately 6 years. The study will continue until approximately 127 adjudicated primary endpoint events have been accrued in unique subjects, or until the Sponsor (eg, based on advisement by the Data Monitoring Committee; DMC) terminates the study.

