13.1. Efficacy Analysis

13.1.1. Analysis Populations

The following subject populations will be evaluated and used for presentation and analysis of the data:

- The Intent-to-Treat (ITT) Population will include all randomized subjects who receive any amount of investigational product (OCA or placebo). The ITT Population will be the primary population used for efficacy analyses. Treatment assignment will be based on the randomized treatment.
- The Per Protocol (PP) Population will include all ITT subjects who do not have any major protocol violations that potentially affect the efficacy conclusion. Treatment assignment will be based on the randomized treatment.
- The Safety Population will include all subjects who received any amount of investigational product (placebo or OCA). The Safety Population will be the primary population used for safety analyses. Treatment assignment will be based on the treatment actually received.
- The PK Population will include all OCA subjects who have at least one confirmed fasted analyzable sample. Subjects must have been fasting for approximately 8 hours prior to the visit and must not have any major protocol deviations that potentially affect exposure levels. The PK population will be used for OCA PK analyses.
- The Overall Historical Control Population will include subjects from the United Kingdom (UK) -PBC Group and Global PBC Study Group databases with demonstrated comparability to randomized subjects in this clinical study (747-302) with respect to both subject characteristics and disease progression.
- The UK-PBC Historical Control Population will include subjects from the UK-PBC Group databases with demonstrated comparability to randomized subjects in this clinical study (747-302) with respect to both subject characteristics and disease progression.

- The Global PBC Historical Control Population will include subjects from the Global PBC Study Group database with demonstrated comparability to randomized subjects in this clinical study (747-302) with respect to both subject characteristics and disease progression.

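### Section 13.1.8 tests OCA against historical controls within propensity score quintiles but takes the hazard ratio from a Cox model stratified by randomization strata, which historical subjects do not have

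*Protocol*

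**What the plan says.** Section 13.1.8 plans a propensity score from a logistic model and forms strata from it: "quintiles of the estimated propensity score from the combined group will be used to determine the stratum boundary cut-offs". The test follows from this: "The propensity score quintile will be then be used as the stratification factor in the stratified log rank test to compare randomized OCA-treated subjects". Those subjects come from the ITT population, and the comparator is the Overall Historical Control Population. Five outcomes built from death and liver transplant are compared.

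The estimate for the same comparison is specified differently: "The hazard ratio and 95% CI will be determined based on a Cox regression model stratified by randomization strata to estimate the magnitude". Section 13.1.3 uses the same sentence for OCA versus placebo. The randomization strata are defined in section 7.1: "Randomization will be stratified by UDCA treatment (yes/no) and baseline bilirubin categories", that is, two binary factors and four cells.

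Three other passages bear on the point:

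- Section 13.1.1.1 says that propensity score matching will select the historical controls, and 13.1.8 mentions a matched dataset with balance checks.
- Section 13.1.1 defines each of the three historical populations as subjects "with demonstrated comparability to randomized subjects in this clinical study (747-302) with respect to both subject characteristics and disease progression".
- Section 13.1.8 states: "Only covariates and not outcome variables will be included in the propensity score estimation".

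**The concern.** The Cox model cannot be fitted as literally written, because one of the two groups has no value for the stratification variable. If someone supplies that value by classifying historical subjects on UDCA use and bilirubin, two factors stand in for the broad covariate set that 13.1.8 considers necessary to limit bias.

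The p-value and the hazard ratio reported side by side would then come from differently adjusted analyses and could disagree. If the controls entering the model are not matched, the hazard ratio could also carry residual confounding that the quintile strata would have removed.

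This is not a detail left to the SAP. Section 13.1.8 defers the list of covariates, but it fixes the Cox strata itself, so an SAP must either repeat the slip or depart from the protocol. Section 13.1.8 also allows similar methodology in a possible revised primary analysis of OCA against placebo plus historical controls, subject to prior regulatory agreement.

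**Working it through.** **Plan's own figure.** The historical comparison has no stated power or effect size to reproduce. The randomized design figures in 13.1.2 do reproduce: 127 events at HR 0.60 give 82% power for a fixed design and 81% with the two interim looks. For sample size, 127 / 0.331 = 384 and 384 / 0.9 = 427, against 428. They do not bear on this point, except that 428 / 2 = 214 OCA subjects is used below.

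**Side by side.**

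| Item | Randomized comparison (13.1.3) | Historical comparison (13.1.8) |
|---|---|---|
| Log-rank strata | Randomization factors | Propensity score quintile |
| Cox strata | Randomization strata | Randomization strata |
| Do both groups have the Cox strata? | Yes | No; historical subjects are outside the study |

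Test and estimate agree in the first column and disagree in the second.

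**Could the strata be derived?** Probably. Section 13.1.8 says the databases hold UDCA use, and 13.1.1.1 says they hold longitudinal liver biochemistry (bilirubin is not named). No rule for deriving the strata is given.

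**What would then adjust the hazard ratio?** Matching, if the matched set is analysed, plus UDCA and bilirubin category. No propensity term enters the Cox model.

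**Which set is analysed?** Section 13.1.1.1 points to matched controls. The log-rank sentence in 13.1.8 names the Overall Historical Control Population, whose definition in 13.1.1 does not mention matching. Section 13.1.8 also lists matching, stratification and regression adjustment as possible uses of the score, alone or combined.

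**Illustrative size.** All inputs except the 214 and the 6 to 10 years of follow-up are assumptions:

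- 214 OCA and 2000 historical subjects; true HR 1.00.
- Severity x is normal with SD 1 and is worse by 0.25, 0.5 or 1.0 SD in the historical group.
- High bilirubin (b = 1) if x plus standard normal noise exceeds 0.3; UDCA use 90% in both groups.
- Hazard = 0.06 × exp(0.5x + 0.4b) per year; follow-up uniform on 6 to 10 years.
- Logistic propensity score on x, b and UDCA, so every confounder is measured.
- 400 replicates per setting; Monte Carlo standard error 0.005 to 0.007 on the log scale.

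Average hazard ratio (the truth is 1.00):

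| Controls | Shift (SD) | Unstratified | UDCA × bilirubin strata | Propensity quintile strata |
|---|---|---|---|---|
| Unmatched | 0.25 | 0.87 | 0.92 | 0.99 |
| Unmatched | 0.5 | 0.76 | 0.85 | 0.97 |
| Unmatched | 1.0 | 0.58 | 0.73 | 0.94 |
| 1:1 matched | 0.25 | 1.01 | 1.01 | 1.01 |
| 1:1 matched | 0.5 | 1.00 | 1.00 | 1.00 |
| 1:1 matched | 1.0 | 1.00 | 1.00 | 1.00 |

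Share of the log-scale bias removed without matching = 1 − ln(HR stratified) / ln(HR unstratified), computed from the three-decimal results:

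- Randomization-factor strata, shift 0.5: 1 − ln 0.851 / ln 0.760 = 1 − 0.161 / 0.274 = 41%. The other shifts give 42% (0.25) and 40% (1.0).
- Quintile strata, shift 0.5: 1 − ln 0.974 / ln 0.760 = 1 − 0.026 / 0.274 = 90%. The other shifts give 90% (0.25) and 88% (1.0).

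**The case against.** The strongest reply is that adjustment happens before the Cox model. Section 13.1.1.1 selects controls by propensity matching under the trial's own eligibility criteria. Section 13.1.8 adds standardized differences, variance ratios and box plots to check balance, and gives modelling and matching to independent statisticians. With good matching, all three models in the table agree at 1.00 to 1.01. This stands. A reader might infer that the hazard ratio is not adjusted for confounding at all, or keeps nearly all of it, and the documents do not support that. Matching is planned, and even without it derived UDCA and bilirubin strata removed about 40% of the bias in the illustration.

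The comparison is also supportive. Section 5.5.2.3 keeps it separate from the placebo comparison, and it lies outside the testing hierarchy of 13.1.10. That stands too, and it limits the consequence.

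Neither reply cures the specification. The stratification variable is still undefined for one group, the test and the estimate still use different strata, and the analysed set is still not named.

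A reader might also take the words on disease progression in 13.1.1 to mean that controls are selected on outcome, since section 6.2 treats disease progression as something OCA may affect. The text does not establish this. Section 13.1.1.1 puts comparability into effect through eligibility criteria and covariates, and 13.1.8 keeps outcome variables out of the propensity score. The wording is loose and worth clarifying, but selection on outcome is not shown.

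**Conclusion.** The specification is wrong as written and needs correcting. For one comparison, the log-rank test uses propensity quintiles, while the hazard ratio and its interval use strata that historical subjects never received. The Cox model itself carries no propensity adjustment.

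This rests on the text alone. The size of any bias is conditional. It can be material if unmatched historical controls are analysed: null hazard ratios of 0.92, 0.85 and 0.73, against 0.99, 0.97 and 0.94 with quintile strata. It is close to nil after good 1:1 matching. Those values depend on assumed imbalances, on historical subjects being the sicker group, and on every confounder being measured. They illustrate the mechanism and do not predict the trial's result.

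The OCA-placebo primary and key secondary analyses are unaffected. The point would gain weight if the revised primary analysis that 13.1.8 allows were ever adopted.

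**What to change.** 1. In 13.1.8, replace *randomization strata* with *propensity score quintile* in the Cox sentence, so that the hazard ratio, its interval and the log-rank test share one adjustment.
2. In the same section, state whether the matched set or the whole Overall Historical Control Population is analysed and, if matched, how the matching is accounted for.
3. As a secondary clarification, in the three historical population definitions of 13.1.1, say that comparability is judged on baseline eligibility and baseline covariates, including baseline disease stage, and not on progression after baseline.

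These are wording changes to the protocol, to be carried into the SAP. They need no new data and alter no design figure.
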